Subjects will receive conservative standard of care treatment plus two ITU treatments (week 0 and week 4) on the affected CET (figure 2) using the ultrasound therapy device. Treatments will be up to 10 minutes in duration. A 2, 4, and 8 week follow up period will be included to monitor the effects of the therapy post treatment. A 12 and 24-26 week telephone assessments for the primary objectives will also be included. Telephone assessments will consist of the subjects answering the survey questions over the phone.

Subject self-assessments will be conducted before the treatment phase and during the follow-up period. Physical exams will be completed by a physician. Physical therapy will be completed by a therapist. ITU treatment and diagnostic ultrasound will be performed by Guided Therapy personnel as shown in the full schedule of events (Appendix 1).

[figure not shown]

Figure 2: Treatment Area

SELECTION OF SUBJECTS**Planned number of subjects**

The study population will consist of up to 25 subjects with unilateral CET tendinosis defined as pain lasting more than 3 months with little or no improvement following conservative standard of care alone.

The selection of suitable subjects will be made according to the inclusion and exclusion criteria described in the following sections.

Inclusion Criteria

1. Subjects who are in general good health and are willing to cooperate and participate by following study requirements for the duration of the study, and to report any adverse symptoms immediately;
2. Subjects who have provided written and verbal informed consent;
3. At time of enrollment subjects are between the ages of 21 and 65 years
4. Subjects literate in English and able to complete all patient self-assessment questionnaires;

5. Subjects is willing to refrain from beginning any additional treatment during the duration of the study;
6. Subjects is willing to refrain from changing physical activity during the duration of the study;
7. Subjects diagnosed with unilateral CET tendinosis defined as pain lasting more than 3 months with little or no improvement following conservative standard of care alone.
8. Subjects with BMI ≤ 35 or at the discretion of the PI.
9. Subjects must be able to sit in a chair with their arm on an appropriate table for the treatment and diagnostic ultrasound imaging.
10. Subject must be able and willing to complete the at home therapy regimen.

Exclusion Criteria

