Diagnostic Ultrasound Imaging will be performed by a trained Sonographer using the Spark® Imaging System, manufactured by Ardent Sound, Inc., Mesa, AZ USA (Appendix 7-B)

Subjects will be imaged seated with their arm resting on a structure that is comfortable for the subject and sonographer.

PolySonic® or AquaSonic® Gel will be applied by the sonographer as required to maintain adequate acoustic coupling. (Appendix 7-C)

1

[figure not shown]
Images will be preserved with the following notations:

- Protocol ID
- Right vs. Left CET Tendon
- Treated vs. Untreated

Long Axis and Short Axis (if necessary) images will be stored at the Sonographer's discretion, to demonstrate and track the applicable anatomy/pathology in the peri-CET area.

Sonographer will also measure the thickness of the CET tendon in each applicable image.

Sonographer will scan the contralateral CET tendon in the same manner noting the change in the tendon (Right v. Left) and (Treated v. Untreated).

Common Extensor Tendon
Figure 4: representative long axis ultrasound images

Outcome measures

Subjects will complete subject reported outcome measures at 0, 2, 4, 8, 12, and 24 weeks and will undergo a focused physical examination and diagnostic ultrasound at 0, 2, 4, and 8 weeks. Adverse events will be recorded at each visit. Treatment tolerability will be assessed immediately after each treatment using the Visual Analog Scale for Pain (VAS) or Universal Pain Assessment Tool (Appendix 3-B). The VAS will be used for 2 different assessments: 1. Pain related to physical activity of the symptomatic arm before treatments and at follow-up visits and phone surveys. 2. Pain tolerance of the therapy treatment. Each of these assessments will be documented and evaluated separately.

Aim 1: reported outcomes

The principal aim of this study is to assess the efficacy of treatment and time course of response to treatment using validated subject reported outcome measures assessing pain, function and level of activity. Subjects will complete validated subject reported outcome questionnaires assessing pain, function and level of activity prior to initiating treatment and at

0, 2, 4, 8, 12, and 24 weeks after starting treatment (Appendix 2 and 3A).

Clinical Pain and Treatment Tolerance will be assessed using the Visual Analog Scale for Pain (VAS) or Universal Pain Assessment Tool (Appendix 3-B).

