Additionally SAEs must be reported immediately to the IRB Title with 24 hours of the site staff becoming aware of the event. The contact details for reporting any expedited AE are given in the Contacts section of this protocol.

In the event that the percent of study related AEs is $\geq 25\%$ for a specific AE symptom, the IRB Title should be notified within 24 hours.

FOLLOW-UP OF ADVERSE EVENTS

If an AE is ongoing at the end of the study, follow-up will be performed until the AE has resolved. Follow-up may take the form of subject visits, a referral to another specialist, site telephone calls to the subject or letters from the treating physician.

The PI or designee must comply with the specific reporting requirement(s) of the ethics committee.

PREGNANCY

Females may not participate in this study if they are pregnant, breastfeeding, were pregnant or gave birth within the last three months or are planning a pregnancy during the course of the study.

GUIDED THERAPY SYSTEMS, CONFIDENTIAL

If the subject thinks they have become pregnant during the study it is important that they inform the study doctor immediately. If the subject becomes pregnant or thinks that they may be pregnant, they will be removed from the study.

STATISTICAL CONSIDERATIONS

SAMPLE SIZE CALCULATION

Up to 25 subjects will be enrolled onto the study to ensure a minimum of 25 subjects complete.

STATISTICAL METHODS

A sample size of 25 per protocol subjects will be required to demonstrate statistical significance (two-sided alpha=0.05; 80% power). Descriptive statistics will be calculated for comparison to the values noted in the existing literature.

MONITORING

The PI agrees that the site will permit, if required, study-related monitoring, audits, IRB/IEC review, and regulatory inspection(s), providing direct access to source data/documents.

Sponsor personnel, or their designees, may monitor the study. The monitor has the responsibility to familiarise the PI and the entire centre staff involved in the study with Therapy procedures. The monitor can visit the clinical study centre on a regular basis such as before the first subject has been enrolled, during the course of the study, and at study completion. The monitor must maintain the confidentiality of the study documents. Regular visits may be made to monitor clinical procedures throughout the study duration.

DATA HANDLING AND RECORD KEEPING

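### Tendon thickness, the only instrument-measured efficacy endpoint, is read with arm and visit known and with no written image-acquisition rule; a coded, random-order read would reduce the bias but not remove it

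*Protocol*

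**What the plan says.** **Who treats and images.** The protocol's Study Outline states that "ITU treatment and diagnostic ultrasound will be performed by Guided Therapy personnel", and Appendix 1 assigns both tasks to the sponsor. The Aim 2 paragraph allows a sonographer or a physician and names no employer. These statements need reconciling.

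**How images are kept and measured** (protocol, Diagnostic Ultrasound Imaging).
- "Treated vs. Untreated" is one of three notations on preserved images. The others are the protocol ID and right or left. Visit is not listed.
- "Long Axis and Short Axis (if necessary) images will be stored at the" sonographer's discretion.
- "Sonographer will also measure the thickness of the CET tendon in each applicable image".
- The other arm is scanned and change is noted by treatment status: "Sonographer will scan the contralateral CET tendon in the same manner noting the change in the tendon (Right v. Left) and (Treated v. Untreated").

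**How the values are used.** Assessment of Efficacy makes thickness a secondary endpoint, alongside a physical examination. Aim 2 applies paired t tests at the 0.05 level to pre- and post-treatment thickness in the treated and untreated arms. The Reporting and Publication Policy gives the statistical analysis to the sponsor. The SAP has no thickness analysis.

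**What the surviving text does not contain.** It describes no masked, central, second or repeat reading, no fixed measurement site and no fixed number of images. The emergency code-breaking section mentions treatment codes, but every subject is treated on the known symptomatic arm, so it does not mask the person measuring.

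**The concern.** All primary endpoints (PRTEE, SROM, VAS) are self-reported by subjects who know they were treated. Thickness is different in two ways: it is measured on an instrument with an untreated arm in the same subject as comparator, and it leaves a stored record that can be read again without knowing arm or visit.

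That advantage depends on both arms and all visits being read alike. Here the person who selects the frame and places the calipers knows both facts and is asked to note the change by treatment status. An expectation that the treated tendon will thin can act on the choice of image, the measurement point and the caliper position. The risk is a nominally significant thickness result in Aim 2 that partly reflects reading rather than tissue.

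**Working it through.** **1. The plan's own figure.** The protocol says "A sample size of 25 per protocol subjects will be required to demonstrate statistical significance" ("two-sided alpha=0.05; 80% power"). No endpoint, effect size or SD accompanies the 25, so it cannot be reproduced. Back-solving for one paired comparison gives the standardised difference that 25 pairs can detect:
- normal approximation: (1.960 + 0.842)/√25 = 2.802/5 = 0.56;
- noncentral t with 24 df: 0.58.

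**2. What the paired design cancels.** Write β(arm, visit) for the average reading error, with T treated and U untreated. The Aim 2 wording leaves open which paired difference is tested. The error carried into each candidate is:

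| Comparison | Error that remains |
|---|---|
| Change within the treated arm | β(T, post) − β(T, pre) |
| Treated minus untreated arm, post-treatment | β(T, post) − β(U, post) |
| Difference in change between arms | [β(T, post) − β(T, pre)] − [β(U, post) − β(U, pre)] |

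An error that is the same for both arms and all visits cancels in all three. Drift over visits shared by both arms cancels in the second and third. An error confined to the treated arm after treatment, which is the form that expectation would take, remains in full in all three.

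**3. Effect on the false-positive rate (illustration).** Inputs: n=25, two-sided 0.05, no true change, all 25 subjects contributing. Let b be the differential shift divided by the SD of the paired difference. This is assumed; the documents give no measurement error. The test statistic is noncentral t with 24 df and noncentrality b√25 = 5b. The false-positive rate is P(|t| > 2.064).

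| Assumed b | 5b | False-positive rate |
|---|---|---|
| 0 | 0 | 5.0% |
| 0.1 | 0.5 | 7.7% |
| 0.2 | 1.0 | 16.1% |
| 0.3 | 1.5 | 30.2% |
| 0.4 | 2.0 | 48.4% |

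Nearly all rejections fall in the direction of the shift: at b=0.2, 15.9 of the 16.1 percentage points.

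**4. Selective storage (a second illustration).** Suppose the thinnest of k images is kept after treatment only, and the image-to-image SD is r times the SD of the change. Then b = r × |expected minimum of k standard normals|, where that expectation is about 0.56 for k=2 and 0.85 for k=3. Selection is treated as a pure shift, and its effect on the variance is ignored.

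| k | r | b | False-positive rate |
|---|---|---|---|
| 2 | 0.25 | 0.141 | 10% |
| 2 | 0.5 | 0.282 | 27% |
| 3 | 0.25 | 0.211 | 17% |
| 3 | 0.5 | 0.423 | 53% |

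**5. Size of a masked read.** Appendix 1 schedules imaging at weeks 0, 2, 4 and 8, so 25 subjects × 2 elbows × 4 visits = 200 elbow-visit sets.

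**The case against.** Several stronger readings are tempting, and the documents do not carry them.

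- **That thickness is the only objective efficacy measure.** The secondary endpoint also includes a physical examination, which covers elbow range of motion. Thickness is the only instrument-measured endpoint. The examination is clinician-assessed, and no masking is described for it either.
- **That the treatment-status notation is the cause.** It tells the person scanning nothing new, since the symptomatic arm is the treated one. It matters because it would unmask a later reader. For pre/post change, hiding visit matters more.
- **That masking would remove the bias.** Whoever holds the probe still knows arm and visit. Visible pathology may reveal the symptomatic side, and a person re-reading their own scans may remember them.
- **That the protocol has no measurement site.** Some figures are not shown and may mark one. The claim is limited to the surviving text.
- **That thickness images are selectively kept.** The discretion sentence concerns tracking anatomy and pathology and may cover documentary views only. Aim 2 separately calls for thickness at each documented assessment. Selective storage is possible under the wording, not stated by it.
- **That the real false-positive rate is 16% to 48%.** Those figures rest on an assumed shift; at 0.1 SD the rate is 7.7%. A shift common to both arms would cancel in a between-arm comparison of change.

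It is also fair to say that the impact is bounded: the principal aim is patient-reported, thickness is secondary, and the SAP does not analyse it.

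These points narrow the concern without answering it. Nothing in either document protects the reading from knowledge of arm and visit, and the readings still go to a significance test.

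**Conclusion.** The concern holds in this limited form. Thickness readings for Aim 2 are unmasked, they are taken by personnel of the sponsor that also delivers the treatment, and the surviving text has no fixed acquisition rule. Differential reading error would pass into the paired t tests.

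Its size is unknown. The percentages show only how sensitive a 25-pair test is. A shift of 0.2 SD, about a third of the difference the test can detect with 80% power (0.2/0.58 = 0.34), would roughly triple the 5% error rate (16.1/5.0 = 3.2). They assume no true change, a constant shift and 25 complete pairs; the protocol allows for no dropout ("Up to 25 subjects will be enrolled onto the study to ensure a minimum of 25 subjects complete").

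The change is worth making because it is cheap, but it protects a secondary endpoint and only in part. That sponsor staff perform the imaging follows from the Study Outline and Appendix 1. The Aim 2 wording on who images is looser and should be brought into line.

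**What to change.** 1. **Acquisition.** In Diagnostic Ultrasound Imaging, require a set of long-axis images per elbow per visit, with the number fixed in advance and taken at one stated landmark. Store all of them. Extra views for pathology can stay discretionary.
2. **Coding.** On the files to be measured, replace the treated/untreated and right/left notations with a code. Hold subject, side, visit and treatment status in a separate linkage key.
3. **Reading.** After week 8, have imaging staff already in the study measure all coded files in random order with subject, side and visit hidden. Preferably this is not the person who scanned, if someone else is available; the documents do not show whether anyone is.
4. **Analysis.** State in Aim 2 that these masked values enter the paired t tests, and which paired difference is tested.
5. **Consistency.** Reconcile the Study Outline and Appendix 1 with Aim 2 on who performs the imaging.

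**Cost.** File coding, a linkage key, one batch read of about 200 elbow-visit sets, and no thickness values for analysis until after week 8. No added visit, scan or subject is needed, and the documents tie no treatment decision to thickness.

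**What remains.** Acquisition stays unmasked, visible pathology may give away the symptomatic side, and recall is possible if the person who scanned also reads. The report should state these limits.

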Subjects may discontinue from the clinical study at any time. In addition, the Principal Investigator (PI) or designee has the right to withdraw a subject for any reason that is in the best interests of the subject. The subject must inform the Investigator immediately if they intend to withdraw. Subjects may be asked to come to the study facility to complete some end of study procedures.

The Investigator can remove the subject from this study without their consent for any reason, including, but not limited to:

- His/her judgment that any condition or circumstance may jeopardize their welfare or the integrity of the study.
- Their failure to follow the instructions of the investigator(s) (protocol non-compliance)
- Subject BMI exceeds ≥ 35 during the courses of the study.
- If the study is stopped by GTS and/or Principal Investigator of the study prior to completion.

CLINICAL ASSESSMENTS

Assessment of Efficacy

Primary:

The primary endpoint(s) for efficacy and tolerability will be the total score of the PRTEE questionnaire (Appendix 2), subject self-assessment of improvement and satisfaction (SROM-Appendix 3-B), and Visual Analog Scale for Pain (VAS) or Universal Pain Assessment Tool (Appendix 3-C).

Secondary:

The secondary endpoint for efficacy will be a measured reduction in tendon thickness by diagnostic ultrasound, and a physical examination.

PRTEE Questionnaire

The PRTEE questionnaire (**Appendix 2**) evaluates three domains clinically relevant to patients (pain, function, and activity) and was specifically developed to assess the clinical severity of CET tendinopathy. It is composed of 15 questions that cover 3 domains of pain (questions 1 through 5), function for specific activities (questions 6 through 11), and general activities (questions 12 through 15). All questions are scored 0 – 10. Higher scores indicate more severe CET tendinopathy. The PRTEE questionnaire has been validated and shows good test-retest reliability¹⁸

Physical Examination

Medical History: Review patient's medical history questionnaire. Review any diagnostic imaging, tests, or work up listed under longitudinal medical record and centrality. Ask about possible trauma or history of injuries to the symptomatic arm. Review athletic history (tennis, golf, etc) and subject's pre-study exercise regimen (if any). Height, Weight (BMI) will also be documented.

History of Present Illness: Most common complaint is of elbow pain.

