Function will be assessed using three validated response forms: PRTEE - An index of the severity of CET Tendinopathy¹⁸ (Appendix 2), Self-Reported Outcome Measures (SROM)¹⁶.

Level of Activity will be assessed using the activity subscale of PRTEE¹⁸ (Appendix 2). This subscale scores quantitatively the level of difficulty subjects face when they perform basic activities of daily living. It has shown to be an accurate and reliable predictor of the activity level while performing day-to-day activities.

Statistical analysis

Data will be assessed for variance homogeneity and normality. PRTEE¹⁸, and Visual Analog Scale for Pain (VAS) or Universal Pain Assessment Tool (Appendix 3-B) scores will be assessed before and after intervention. The VAS will be used for 2 different assessments: 1. Pain related to physical activity of the symptomatic arm before and after treatment. 2. Pain tolerance of the therapy treatment. Each of these assessments will be documented and evaluated separately.

Aim 2: CET Tendon thickness

Diagnostic ultrasound imaging will be performed with an FDA approved ultrasound scanner (Spark[®] System, Ardent Sound, Inc. – Mesa, AZ, see Appendix 7-B using a coupling gel (Polysonic[®], or AquaSonic[®], Parker Laboratories, Inc., Fairfield, NJ, see Appendix 7-C) by a trained sonographer or physician. Subjects will be treated seated with their arm resting on a structure that is comfortable for the subject and technologist.

CET Tendon thickness is measured before treatment(s) and at each documented assessment (Appendix 1). Paired t tests are used to compare the CET Tendon thickness means between pre- and post-treatment between the symptomatic and treated arm and the asymptomatic and untreated arm. P<0.05 is considered to be statistically significant. Any peri-CET pathology will also be documented.

Aim 3: Assessment of safety and tolerability

Subject self-assessments of treatment tolerability will be conducted immediately after treatments, and at each follow-up visit and phone survey using a 10-point visual analog scale VAS, (Appendix 3-B). The subject will be asked to report their current level of pain and the maximum level of pain experienced since the last treatment. The surveyor will remind the subject of the VAS criteria and record their reply. The VAS is the standard for assessing pain for both clinical and research purposes²².

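### The tendon-thickness test fixes neither the contrast nor the visit; name one difference-in-change test at week 8 and say that it cannot isolate ITU

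*Protocol*

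**What the plan says.** The protocol section on Aim 2 gives the whole analysis in one sentence: "Paired t tests are used to compare the CET Tendon thickness means between pre- and post-treatment between the symptomatic and treated arm". The second member of that comparison is the same subject's opposite elbow, described as "the asymptomatic and untreated arm". The threshold follows: "P<0.05 is considered to be statistically significant". No adjustment for multiple tests is given.

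The endpoint itself, under Assessment of Efficacy, is no more specific: "The secondary endpoint for efficacy will be a measured reduction in tendon thickness by diagnostic ultrasound", with no contrast and no visit. Outcome measures schedules "diagnostic ultrasound at 0, 2, 4, and 8 weeks", so there are three post-baseline images. Assessments at Each Visit places imaging before each treatment. The week 4 image therefore comes after the first treatment and before the second.

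Both elbows are imaged (Ultrasound Imaging). The disease is unilateral by inclusion criterion, and every subject has conservative standard of care as well as ITU (Study Outline). The SAP covers VAS pain and PRTEE only and does not mention tendon thickness.

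**The concern.** A paired t test needs one defined pair. The protocol sentence joins a before/after comparison to an arm/arm comparison and admits three constructions:

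- **(a)** before against after, separately within each arm;
- **(b)** treated arm against untreated arm at a post-treatment visit;
- **(c)** change in the treated arm against change in the untreated arm.

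These answer different questions. Construction (a) measures change under ITU plus standard of care. Setting a significant treated arm beside a non-significant untreated arm is not a comparison of the two. Construction (b) compares a diseased tendon with a healthy one, whatever treatment did. Construction (c) is the nearest to the aim.

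This is the only analysis in either document with a named significance test and its own P-value threshold. The opposite arm is the only internal comparator in a study described as controlled. A positive thickness result would therefore probably be read as controlled evidence, with contrast and visit still open to choice once the data are seen.

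**Working it through.** **Inputs from the documents.** n = 25 (Statistical Methods: "A sample size of 25 per protocol subjects will be required to demonstrate statistical significance"), with "two-sided alpha=0.05; 80% power"; P<0.05 per thickness test; three post-baseline images. No SD, effect size or correlation for thickness is given, so all of those below are assumptions.

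**1. The plan's own figure.** N = 25 cannot be reproduced, because no effect size or SD is stated and the figure is not tied to thickness. Worked backwards for one paired t test, the normal approximation gives (1.960 + 0.842)/√25 = 0.560. The noncentral t gives 0.584 SDs of the paired difference.

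**2. Construction (a): treated significant, untreated not.** Suppose both tendons truly change by the same amount and each arm's test has power p. With independent arms the probability is p(1 − p):

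- p = 0.8: 0.8 × 0.2 = 16%
- p = 0.5: 0.5 × 0.5 = 25%

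Two tendons in one person are unlikely to be independent. Simulation at n = 25 with correlated changes gives:

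| Correlation of the two arms' changes | p = 0.8 | p = 0.5 |
|---|---|---|
| 0 | 16% | 25% |
| 0.3 | 14% | 21% |
| 0.5 | 12% | 17% |
| 0.8 | 7% | 11% |

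A direct two-sided 5% test of the difference in change errs in that direction 2.5% of the time.

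**3. Construction (b) with no treatment effect.** Assume thickness SD 1, within-arm correlation over time 0.8 and between-arm correlation 0.5. The variance of the arm difference at a visit is 2(1 − 0.5) = 1, so a baseline arm difference is already in SD units of the test. Simulated week 8 rejection rates are 22%, 67%, 95% and 99.8% for baseline differences of 0.25, 0.5, 0.75 and 1.0 SD. The failure also runs the other way: a true reduction of 0.5 SD that brings the treated tendon level with the other is detected 5% of the time by (b), against 77% by (c).

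**4. Construction (c) with no ITU effect, same assumptions.** If the same drift occurs in both arms, rejection stays at 5%. If drift occurs only in the symptomatic arm, rejection is 8%, 19%, 37% and 77% for drifts of 0.1, 0.2, 0.3 and 0.5 SD. In this model the two arms' changes are uncorrelated.

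**5. Visits.** If one contrast were tested at all three visits without adjustment, independent tests would give 1 − 0.95³ = 14.3%. With correlation between the tests of 0.3, 0.5 and 0.7, simulation gives 13.7%, 12.7% and 11.1%, two-sided. Counting only false reductions, the corresponding range is about 7.0% down to 5.6%, against 2.5%.

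**6. Precision of (c).** With equal variances σ² of change in each arm and correlation r between them, the variance of the difference in change is σ² + σ² − 2rσ² = 2(1 − r)σ². That is 2σ² at r = 0, σ² at r = 0.5 and 0.4σ² at r = 0.8.

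**The case against.** The strongest reply is that the sentence, though clumsy, already means (c): its doubled between reads naturally as before/after change compared between arms. Diagnostic Ultrasound Imaging helps this reading, because the sonographer is told to scan the opposite tendon in the same manner and note change by side and by treatment. That is partial support. It is an imaging instruction and does not define a test, and the plural tests remain without a visit. No passage sets a rule that treated significant and untreated not counts as success, so the risk in (a) is one that the wording permits and does not prescribe.

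Three further objections stand:

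- A reader might infer from the imaging schedule that every visit will be tested. The documents say that thickness is measured at those visits; the test visit is simply unspecified. The 11-14% is conditional on testing all three.
- The 16-25% requires independent arms and a healthy, untreated tendon that changes enough to give 50-80% power. No passage supports such a change, and correlation lowers the rates. With no change in either arm there is no inflation.
- A reader might infer that (c) is a clean test of ITU. It is not. The comparator tendon is asymptomatic and every subject has standard of care, so recovery, regression to the mean or exercise response in the symptomatic arm alone would still count as effect. Appendix 6-A itself expects the exercises to relieve pain in most cases in about 4 to 6 weeks, inside the imaging window.

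**Conclusion.** The point holds as a failure to specify the contrast and the visit, at an unadjusted threshold, with no help from the SAP. Two of the constructions that the wording allows can give a false treatment claim. Arm against arm mostly registers the disease side. Separate within-arm tests produce the misleading pattern 7-16% of the time at per-arm power 0.8 and 11-25% at power 0.5, over assumed between-arm correlations from 0.8 down to 0, provided that both tendons truly change equally. Difference in change is the best available contrast, but none of the three isolates ITU.

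It would go too far to conclude that the trial's main result is compromised: thickness is a secondary endpoint, and the principal aim rests on patient-reported measures. Nor do the documents show that any particular wrong test will be run. The change should be made before thickness is analysed. It is not critical to the primary conclusion.

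**What to change.** Replace the Aim 2 sentence with:

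> At week 8, one paired t test (two-sided 0.05) compares, within subject, the change from week 0 in the treated tendon with the change from week 0 in the untreated tendon, (T8 − T0) − (U8 − U0), reported with a 95% CI. Weeks 2 and 4 and within-arm changes are descriptive. This contrast removes only drift common to both arms. Because the comparator tendon is asymptomatic, it cannot separate ITU from natural recovery, regression to the mean or co-treatment in the symptomatic arm.

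Repeat the definition in the SAP. Week 8 is proposed because it is the only imaging visit after both treatments.

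No new data are needed, since both arms are already imaged at weeks 0 and 8. The cost in precision depends on r: the difference in change is less precise than a within-arm change when r < 0.5 and more precise when r > 0.5. At n = 25 the detectable standardised difference at 80% power is about 0.58, in SDs of the difference in change. That assumes all 25 subjects supply both week 0 and week 8 images, and the plan has no margin for loss: "Up to 25 subjects will be enrolled onto the study to ensure a minimum of 25 subjects complete".
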